8.2. Recording and Reporting Procedures

Any questions concerning adverse event reporting should be directed to the Sub Investigator or Chief Investigator in the first instance.

All adverse events/reactions

All AE/AR should be recorded on the dedicated CRF at the earliest opportunity following the trial team becoming aware of the event. This is most likely to be during the regular follow-up visits. The CRF will detail the date/time of the event and any actions

Serious adverse events/reactions

Any events that meets the criteria for an SAE should be discussed with the Sub Investigator or Chief Investigator. SAEs and SARs should be reported to the sponsor within 24 hours of the Sub Investigator or Chief Investigator becoming aware of the event, using the separate Sponsor-specific SAE.

Events which are serious, causally related to a trial procedure (in the opinion of the C.I), and which are unexpected (i.e. a SUSAR) should be reported to the Sponsor immediately upon the trial team becoming aware of the event. The Sponsor has a duty to undertake and co-ordinate the expedited reporting required following such events, including to the approving REC.

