5.5. Blinding

It is impractical to conceal treatments from either patients or healthcare professionals. Therefore, the ACTion trial will be conducted unblinded.

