5.7. Post procedure inpatient period

All patients

Whilst in hospital, all patients will have a clinical review on every working day. As a minimum a chest radiograph will be performed on Day 3 (+/- 1 day) and Day 7 (+/- 1 day), with additional as deemed necessary by the treating physician.

Blood tests should be performed on at least alternate days until day 7, and then at least weekly if the patient remains in hospital.

Thoracic ultrasounds should be performed on day 2 (the day after the first procedure), and then on days 3 (+/- 1 day) and 7 (+/- 1 day), with additional performed as deemed necessary by the treating physician.

Discharge from hospital is ultimately at the discretion of the treating physician. Numerous factors form the basis of this decision to the extent it becomes impossible to protocolise. It is assumed that

as part of good clinical care all aspects of a patient's condition will be assessed before discharge, including clinical status, outpatient follow up and social set up

Control groups

The timing for chest tube removal in the control group is at the discretion of the treating physician. If the chest tube is removed, the patient should have a chest radiograph afterwards.

Interventional group

There may be a requirement for patients to have further therapeutic aspirations if there is reaccumulation of infected pleural fluid. This is an anticipated drawback of this approach and will be explained to the patients as part of the randomisation process. The need for a timing of further procedures will be decided by the treating physician. It is advised they consider the following before making a decision

- clinical/biochemical factors (such as rising CRP/WBC, or fevers).
- Chest radiograph appearances suggesting persisting collections
- Pleural ultrasound appearances suggesting persisting collections as well as the amenability of these collections to drainage

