5.8. Post procedure outpatient period

As dictated above patients will only be discharged if the treating clinician feels they are well enough and will be safe as an outpatient.

Patients in the control arm are likely only to be discharged if their pleural infection has resolved and chest tube has been removed. Patients in the interventional arm, given the nature of the drainage method, have the potential to be discharged before the pleural infection has completely resolved.

The treating physician will have the ability to ask patients from either arm of the study to return early outpatient clinics for repeat blood tests, clinical and radiological review, and even pleural procedures and intravenous antibiotics. It is likely that this service will be utilised more frequently for patients in the interventional arm. As an important part of the ACTion trial's health economic analysis, data will be collected from all patients about the requirement for outpatient hospital visits, primary care attendances, district nurse and social care visits, as burden on informal carers in their home.

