6.2. Imaging

Thoracic Ultrasound

All pleural ultrasounds will be performed as part of standard care. The scan results from the baseline assessment, third (+/- 1 day) and seventh (+/- 1 day) days should be recorded on the electronic trial database. Additionally, the results prior to any pleural procedure that are additional to the above should be recorded as they form part of the reasoning for additional pleural procedures. A pleural ultrasound should also be performed and recorded at the trial follow-ups (Day 30 and 90).

Scans should be performed by those with at least Royal College of Radiologists Level One accreditation (or equivalent).

Chest radiography

All chest radiographs performed during the ACTion trial are part of standard care. Images should ideally be performed as P-A. Whilst an inpatient, chest radiographs should be performed on Day 3 and Day 7, with additional as deemed necessary by the treating physician. They will also be performed after every pleural procedure as part of standard care (including chest tube removal), as well as on trial follow-ups (Day 30 and 90). Given the intervention arm may result in patients having additional pleural procedures there may be an increased number of chest radiographs required in this group. However, the exact number of additional pleural procedures is difficult to predict and forms part of the trial outcomes.

The size of effusion on chest radiograph will be reported by a clinical member of the research team and recorded in the online database.

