7.3. Secondary Endpoint Analysis

Quantitative analysis will focus on obtaining estimates and measures of variation of key unknowns required for the design of a full-scale RCT of TT versus conventional chest tube in pleural infection. We need the following information in order to design an adequately powered trial;

- Descriptive statistics for rates of recruitment, randomisation, attrition, data completion (including differences between the intervention and controls).
- Descriptive statistics for the proposed secondary outcomes (including hospital LOS, number of procedures, readmission rates and surgical referrals), and common adverse clinical events (such as persistent fever, or abnormal blood chemistry and radiography).
- The costs of an ambulatory strategy will need assessing in monetary terms and data on social and NHS costs will be collected here and reviewed by health economic advisors as to their adequacy for use or to identify required amendments for a subsequent full trial.

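### Adverse events are recorded on awareness, with no stated enquiry common to both arms, so the descriptive rates of fever, blood and film abnormalities will partly reflect how closely each arm is watched

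*Protocol*

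**What the plan says.** **Capture.** Protocol 8.2 states: "All AE/AR should be recorded on the dedicated CRF at the earliest opportunity following the trial team becoming aware of the event". It continues: "This is most likely to be during the regular follow-up visits". It does not define those visits, give a prompted list or fix a time at which participants are asked.

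**Common contacts.** Section 5.12 sets trial visits at Day 30 and Day 90, separate from early outpatient visits, with telephone contact for those who cannot attend. For Day 30 it lists the quality-of-life questionnaire, the VAS and a possible interview. For Day 90 it adds clinical assessment, bloods, radiograph, ultrasound and lung function. Appendix 2 mentions a discharge CRF and a Day 90 CRF, but no row names an adverse event enquiry.

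**Contact that depends on allocation.**
- Section 5.7: "Whilst in hospital, all patients will have a clinical review on every working day", and "Blood tests should be performed on at least alternate days until day 7, and then at least weekly if the patient remains in hospital".
- Section 5.8 expects control patients to leave after resolution and tube removal, while thoracentesis patients may leave sooner. Of early outpatient review it says: "It is likely that this service will be utilised more frequently for patients in the interventional arm".
- Section 6.2 requires a film after every pleural procedure and says of the intervention arm that "there may be an increased number of chest radiographs required in this group".

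**Use.** Section 7.3 plans descriptive statistics for "common adverse clinical events (such as persistent fever, or abnormal blood chemistry and radiography"), as information needed to design the full trial. Section 5.5: "Therefore, the ACTion trial will be conducted unblinded".

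**The concern.** A fever, a deranged blood result or a film abnormality becomes an event only if someone measures it. When the number of measurements depends on discharge date and on repeat procedures, and both follow from the allocated treatment, randomisation does not balance the chance of detection. Two arms with the same true risk can then show different rates.

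The rates are intended to inform the design of a full trial of thoracentesis against chest tube. The Trial Steering Committee also reviews safety after ten patients (7.5). With 1:1 allocation that is about five per arm, where one event found only through closer observation moves an arm's rate by 1/5, or 20 percentage points.

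**Working it through.** The protocol gives no adverse event rate, no expected number of tests per arm and no formal sample size (7.1), so there is no stated figure to reproduce. The text settles whether surveillance differs. The arithmetic below only illustrates whether size or direction can be pinned down.

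**1. Does contact differ by arm?** Sections 5.7, 5.8 and 6.2, set side by side, say that it is expected to. Day 30 and Day 90 are common to both arms, but no event question is stated there.

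**2. Bloods (illustration).** Minimum sets on days 1, 3, 5 and 7, then weekly, counted only while an inpatient: discharge on day 3 or 4 gives k = 2; a stay of 7 to 13 days gives k = 4. Section 2.1 quotes a 13-day average stay and 2.3 gives medians of 7 and 10 days for lower-risk groups; the 3 to 4 day stay is an assumption. With an assumed chance q of an abnormality per set, equal in both arms and independent between sets, P(at least one) = 1 − (1 − q)^k.
- q = 0.1: 1 − 0.9² = 19% against 1 − 0.9⁴ = 34%.
- q = 0.2: 1 − 0.8² = 36% against 1 − 0.8⁴ = 59%.

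Three features of the document or of the disease undo this gap:
- Section 6.1 asks for alternate-day bloods in the first 7 days with no inpatient condition. On that reading k = 4 in both arms to day 7 and the gap is zero.
- Appendix 2 includes bloods at early outpatient assessments if none were done within 48 hours. If a patient discharged on day 3 has one, two or three such sets (assumption), k becomes 3, 4 or 5. At q = 0.1 that is 27%, 34% or 41% against 34%: narrower, closed or reversed.
- Repeat bloods in one infected patient are correlated. At the extreme of perfect correlation P = q whatever k is, and the gap vanishes.

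**3. Films (illustration).** Baseline and Day 90 films are common and left out. Procedure films and Day 3 and Day 7 films are counted as separate. For a stay of at least 7 days, control has insertion + removal + Day 3 + Day 7 = 4; thoracentesis has (number of procedures) + 2.

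| Thoracenteses | Films, intervention | P at q = 0.1 | Films, control | P at q = 0.1 |
|---|---|---|---|---|
| 1 | 3 | 27% | 4 | 34% |
| 2 | 4 | 34% | 4 | 34% |
| 3 | 5 | 41% | 4 | 34% |
| 4 | 6 | 47% | 4 | 34% |

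The intervention arm has more films only from the third thoracentesis. If the Day 7 film is not done after discharge, a thoracentesis patient leaving on days 3 to 6 has one film fewer in every row and exceeds a control patient still in hospital on day 7 only at the fourth. Control patients may also need further procedures (8.5), which adds films on their side.

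**4. Do the sections agree on Days 3 and 7?** Section 2.5 presents imaging on these days as a minimum for participants, 6.1 sets bloods for the first 7 days, and 6.3 sets questionnaires on Days 3 and 7 for all. Section 5.7 and Appendix 2 place these assessments in the inpatient period. Which assessments are common to both arms cannot be settled until these sections are reconciled.

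**5. Which events are exposed?** Death, surgery and readmission come to light with little dependence on test frequency. Fever, laboratory, film-detected and minor patient-reported events depend on it.

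**The case against.** **The sentence in 8.2 concerns when the form is completed.** Section 5.12 defines the trial follow-up visits as Day 30 and Day 90, and on that reading "This is most likely to be during the regular follow-up visits" points to contacts that both arms share. This stands in part: the sentence alone does not show unequal capture. But 8.2 does not tie itself to those visits, states no question to be asked there, and leaves inpatient, clinic and procedure-linked detection unequal.

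**The CRFs are not shown.** There is a dedicated adverse event CRF, and 10.2 allows completion from notes or by telephone. So silence in Appendix 2 does not prove that nobody asks. It does mean that the protocol does not require it, and a notes review inherits the contacts and tests that happened to occur.

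**The plan is only descriptive.** In 7.3 the phrase about differences between arms belongs to recruitment, attrition and data completion, not to adverse events. A reader might infer a planned formal comparison of event rates; the text does not support that. The rates are nevertheless listed as inputs to a two-arm trial, and an analysis plan cannot recover events that nobody asked about.

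**Unequal contact is inherent in an ambulatory strategy.** True. Contact cannot be made equal, but a common enquiry and a count of contacts can be had without changing care.

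**A stronger reading is tempting:** that blood and fever events will be over-counted in the control arm and film findings in the thoracentesis arm, by something like 19% against 34%. The documents do not support it. The blood figure needs an assumed short stay, an inpatient-only reading that 6.1 does not share, independent tests and no early-clinic bloods. Two procedure films against four, which would give the same percentages for films, leaves out the Day 3 and Day 7 films and assumes four thoracenteses.

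**Conclusion.** The point holds. Adverse event capture rests on awareness, no common enquiry is stated, and the protocol itself expects contacts and films to differ by arm because of allocation. The rates of fever, abnormal blood chemistry and abnormal radiographs in 7.3 will therefore partly reflect surveillance.

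Net direction and size cannot be derived. The percentages above are illustration only, resting on assumed per-test risks, stays and numbers of procedures or clinic visits. That uncertainty is itself a reason to act, since a reader of the results could not correct for it.

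The consequence is moderate: minor, laboratory and film-detected events in a 30-patient feasibility trial, the safety review after ten patients, and any event rates carried into the full trial. The primary feasibility outcome is untouched.

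**What to change.** **Sections 8.2, 5.12 and Appendix 2.** Put the same short prompted adverse event list to every participant at Day 30 and Day 90, whatever other contact they have had, using the telephone route already in 5.12 for those who do not attend. Add Day 7 once 2.5, 6.1 and 6.3 have been reconciled with 5.7 and Appendix 2 on whether the Day 3 and Day 7 assessments apply after discharge.

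**Section 7.3.**
- Keep all events in the main safety listing. Limiting the main table to common contacts would discard events from a small dataset.
- Mark each event as found at a common scheduled contact or at another contact.
- Show blood and film abnormalities at the days scheduled in both arms. Day 90 qualifies in every section; a Day 30 film appears in 6.2 but not in 5.12 or Appendix 2, so this too needs aligning.
- Report contacts, blood sets and films per arm beside the counts.

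**Cost.** A short checklist at existing contacts, some wording changes and one extra descriptive table. No change to treatment or clinical management is needed.

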8.4. Following reporting

All reported events should be followed to resolution, with additional reports submitted as necessary. This should occur regardless of whether the patient was withdrawn from the trial as a result of the adverse event, unless the withdrawal request rescinded permission for outcome data to be collected and used.

8.5. Expected Adverse Events

The following are considered to be expected in the context of patients suffering with pleural infection and who require an intervention for fluid drainage.

- Chest pain, or discomfort around procedure site (unless not improving or remains unresponsive to analgesia)
- Bleeding associated with trial procedure (unless causing haemodynamic compromise, requiring transfusion, or requiring intervention to achieve haemostasis)
- Subcutaneous infection related to therapeutic thoracentesis or drain insertion, (unless unresponsive to antibiotic therapy)
- Chest drain falling out, becoming dislodged or becoming blocked
- Further pleural procedures required to drain ongoing fluid collection in either control or intervention group
- Pneumothorax or evidence of non-expandable lung following chest drain insertion or therapeutic thoracentesis (unless requiring surgical intervention)
- Hospital admission, elective procedure or surgery, disability, incapacity or death due to underlying or pre-existing condition
- Delay in planned discharge date (unless due to a complication directly related to a trial procedure)
- Readmission to hospital or need for thoracic surgery due to pleural infection or pneumonia
- Hypotension or tachycardia due to sepsis requiring intravenous fluid support alone
- Hypothermia or hyperthermia due to sepsis, within the range $\geq 34.0^{\circ}\text{C}$ to $\leq 39.4^{\circ}\text{C}$
- A reaction to an administered medication (unless not described in the current version of the British National Formulary (BNF))

9. REGULATORY ISSUES

9.1. Research Governance

This study will be conducted in accordance with:

- The International conference for harmonisation of good clinical practice (ICH GCP)
- The Research governance framework for health and social care, and
- The Declaration of Helsinki

9.2. Ethics approval

A research ethics committee will review the trial prior to recruitment commencing. The REC will be asked to approve the trial protocol, GP letter, as well as all “public-facing” or “participant-facing” documentation (e.g. patient information sheet, consent forms, or advertising materials). They will also approve the topic guide to be asked during the semi-structured interview component of the study. All the above will also be approved by the Sponsor.

9.3. Risks and Anticipated Benefits for Participants & Society

Despite the ACTion trial being an investigation of feasibility, there are not expected to be any significant increased risks to individual participants over those associated with the standard clinical care of pleural infection. Both therapeutic thoracentesis and chest tube insertion are considered routine procedures in the management of patients with pleural effusions. Several case series exist documenting the safe and effective use of therapeutic thoracentesis to manage pleural infections in adult and paediatric populations.

The primary potential benefit to those being randomised to the intervention arm in this study is a reduced duration of in-hospital treatment. Should the ACTion trial prove feasible this would lead to a larger fully powered trial. A full-scale trial has the potential to improve the care of patients with pleural infection, as well as better resource allocation within the NHS.

9.4. Sponsor approval

All trial documents will be approved by the Sponsor prior to submission to the REC. Any amendments following a favourable ethical opinion, will be approved by the Sponsor prior to submission to REC.

9.5. NHS approval

Approval from the local NHS Trust (North Bristol NHS Trust) is required prior to recruitment.

Any amendments to the trial documents will be approved by all necessary parties prior to implementation.

9.6. Investigator Responsibilities

This is a single site feasibility trial. The Sub Investigator ([name]) within North Bristol NHS trust will be required to ensure that local research approvals have been obtained and that any contractual agreements required have been signed off by all parties before recruiting any participants. The Sub Investigator will also be required to allow access to study documentation or source data, on the request, for monitoring visits and audits performed by the Sponsor or any regulatory authority.

9.7. Consent

Consent to trial participation must be sought from each potential participant only after a full explanation has been given and a patient information sheet offered. Due to the relatively acute nature of pleural infection, whereby those requiring chest drainage would normally be expected to undergo their procedure as soon as possible, it is not felt practical to mandate participants have 24 hours or more to consider trial entry. However, it is imperative that all participants be given sufficient time (as determined by the participant themselves) for trial information to be considered and for questions to be asked. Signed participant consent should ideally be obtained, but for those patients who are unable to provide a signature an alternative identifying mark (such as a fingerprint) may be used if witnessed by a third party signatory. The right of the participant to refuse to participate without giving reasons must be respected.

For those patients who are approached to have a semi-structured interview, a written confirmation of consent should be sought at the time of questioning. Written consent should also be obtained for any additional party who contributes to the semi-structured interview.

After the participant has entered the ACTion trial, the treating clinician remains free to give alternative treatment to that specified in the protocol at any stage if he/she feels it is in the participant's best interest, but the reasons for doing so should be recorded. In these cases the participants remain within the study for the purposes of follow-up and data analysis. All participants are free to withdraw at any time from the protocol treatment without giving reasons and without prejudicing further treatment.

If a trial participant loses the capacity to consent during the trial then they will be withdrawn from the trial at that point. Data collected with their consent up until the point they lose capacity may be used.

9.8. Confidentiality

The Chief Investigator ([name]), Sub Investigator ([name]), and Sponsor (North Bristol NHS Trust) will preserve the confidentiality of participants taking part in the study in accordance with the Data Protection Act and any other local requirements. Trial documentation and the study database will be anonymised using a unique identification number, generated during enrolment.

No individual participant will be identified in any publications which may arise from this study.

9.9. Indemnity

North Bristol NHS Trust holds standard NHS Hospital Indemnity and insurance cover with NHS Litigation Authority for NHS Trusts in England, which apply to this trial.

